2.5 Confirmation/Duration of response

2.5.1 Confirmation

Objective responses should be confirmed by CT and/or MRI scans obtained no less than 4 weeks after the original scan.

2.5.2 Duration of overall response

The duration of overall response is measured from the time measurement criteria are first met for CR/PR (whichever is first recorded) until the first date that recurrent or progressive disease is objectively documented (taking as reference for progressive disease the smallest measurements recorded on study). The duration of overall complete response is measured from the time measurement criteria are first met for CR until the first date that recurrent disease is objectively documented.

2.5.3 Duration of stable disease

Stable disease is measured from the start of the treatment until the criteria for progression are met, taking as reference the *smallest sum on study* (if the baseline sum is the smallest, this is the reference for calculation of PD).

NCI-CTCAE	National Cancer Institute Common Terminology Criteria for Adverse Events
C _{trough}	Trough concentration
DCR	Disease control rate
DoR	Duration of response
ECG	Electrocardiogram
ECOG	Eastern Cooperative Oncology Group
HPV	Human papilloma virus
ICF	Informed consent form
IHC	Immunohistochemistry
MedDRA	Medical dictionary for regulatory activities
NE	Not evaluable
ORR	Objective response rate
OS	Overall survival
PD	Progressive disease
PD-L1	Programmed death ligand 1

PFS	Progression-free survival
PK	Pharmacokinetics
PPK	Population PK
PR	Partial response
Q3W	Every 3 weeks
QTcF	QT interval corrected by Fridericia method
RECIST v1.1	Response Evaluation Criteria in Solid Tumours version 1.1
SAE	Serious adverse event
SAP	Statistical analysis plan
SCCHN	Squamous cell carcinoma of the head and neck
SPP	Statistical programming plan
SD	Stable disease
SDTM	Study Data Tabulation Model
SOC	System organ class
TEAE	Treatment-emergent adverse event

1 INTRODUCTION

This statistical analysis plan (SAP) provides a detailed and comprehensive description for the analysis of the study CP-MGA271-06 entitled “A Phase 2 Open-Label Trial to Evaluate Enoblituzumab in Combination with Retifanlimab or Tebotelimab in the First-Line Treatment of Patients with Recurrent or Metastatic Squamous Cell Carcinoma of the Head and Neck (SCCHN)”. This SAP Version 1.0 applies to the original protocol of this study and describes in detail the statistical methods to be used for analysis of the primary and secondary efficacy endpoints, the safety endpoints, the pharmacokinetics (PK) and pharmacodynamics parameters to be collected from this study.

2 STUDY OBJECTIVES

2.1 Primary Objectives

Retifanlimab Cohort

- To assess the efficacy of the combination of enoblituzumab + retifanlimab, based primarily upon evaluation of Investigator-assessed objective response rate (ORR) in the response evaluable patient population, in patients with recurrent or metastatic SCCHN not curable by local therapy, with no prior systemic therapy for SCCHN in the recurrent or metastatic setting (with the exception of systemic therapy completed > 6 months prior if given as part of multimodal treatment for locally advanced disease).

Tebotelimab Cohort

- To assess the safety, tolerability, and preliminary efficacy of the combination of enoblituzumab + tebotelimab, based primarily upon evaluation of Investigator-assessed ORR in the response evaluable patient population, in patients with recurrent or metastatic SCCHN not curable by local therapy, with no prior systemic therapy for SCCHN in the recurrent or metastatic setting (with the exception of systemic therapy completed > 6 months prior if given as part of multimodal treatment for locally advanced disease).

2.2 Secondary Objectives

Retifanlimab Cohort

- To evaluate the Investigator-assessed progression-free survival (PFS), disease control rate (DCR), duration of response (DoR), and overall survival (OS).
- To evaluate safety and tolerability.
- To assess the PK of enoblituzumab + retifanlimab.
- To evaluate the immunogenicity of enoblituzumab + retifanlimab.

Tebotelimab Cohort

- To evaluate the Investigator-assessed PFS, DCR, DoR, and OS.
- To assess the PK of enoblituzumab + tebotelimab.
- To evaluate the immunogenicity of enoblituzumab + tebotelimab.

2.3 Exploratory Objectives

Retifanlimab and Tebotelimab Cohorts

- To explore the relationships between PK, pharmacodynamics, patient safety, and antitumor activity.
- To explore population PK (PPK) and exposure-response analyses.
- To explore the relationships between PD-1, PD-L1, B7-H3, and LAG-3 expression on tumor cells and response.
- To investigate the immune-regulatory activity in vivo, including various measures of T-cell and NK-cell activation/exhaustion in peripheral blood and/or tumor biopsy specimens.
- To assess circulating immune cells and effect of treatment.
- To evaluate peripheral biomarkers and correlate with potential clinical response.
- To explore gene expression profiles and Fc receptor polymorphism in PBMCs and/or pre-treatment tumor biopsies and correlate with clinical response (when applicable).

The results of the exploratory objectives may not be included in the Clinical Study Report or database lock unless they represent meaningful findings.

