10 ASSESSMENT OF PHARMACOKINETICS AND PHARMACODYNAMICS

10.1 Pharmacokinetics Assessments

Serum concentrations of enoblituzumab, retifanlimab, and tebotelimab will be analyzed using validated assay methods that will be carried out in the Sponsor's designated central laboratory. Analysis of PK data will be carried out using industry standard software.

Single and multiple dose PK parameters, including but not limited to C_{max} and C_{trough} , will be derived from serum concentration versus time data. PPK and exposure-response analyses will be conducted, using data from this study alone or combined with data from other studies. PPK and exposure-response modeling will be performed, and appropriate models and model parameters will be described. The influence of intrinsic and extrinsic covariates on model parameters will be investigated. The PPK and exposure-response analyses will be the subject of separate reports.

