10.3 Gene Expression Profiling

Gene expression profiling using Nanostring and tumor mutational burden may be determined retrospectively based on response, and prioritized according to the availability of archival and fresh tumor biopsy specimens.

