3.1 Overall Study Design and Plan

This is a Phase 2, open label, non-randomized study in the first-line treatment of patients with recurrent or metastatic SCCHN not curable by local therapy, with no prior systemic therapy for SCCHN in the recurrent or metastatic setting (with the exception of systemic therapy completed > 6 months prior if given as part of multimodal treatment for locally advanced disease).

Approximately 80 patients will be enrolled in 2 cohorts, as shown in **Figure 1**, to receive enoblituzumab in combination with either retifanlimab (Retifanlimab Cohort, PD-L1 positive [CPS \geq 1] patients, N=50) or tebotelimab (Tebotelimab Cohort, PD-L1 negative [CPS < 1] patients, N=30). Enrollment into each cohort will occur in a non-randomized fashion. Patients may not crossover between cohorts. PD-L1 expression will be prospectively collected and prospectively analyzed. B7-H3 and LAG-3 expression will be prospectively collected and retrospectively analyzed.

Figure 1

Study Schema

[figure not shown]
Enrollment in the 2 study cohorts will occur independently in a non-randomized fashion

Dosing Regimens:
 Enoblituzumab: 15 mg/kg Q3W
 Retifanlimab: 375 mg Q3W
 Tebotelimab: 600 mg Q3W

Efficacy Outcomes
Primary: ORR
Secondary: PFS, DCR, DoR, OS

Patients will receive the assigned study drugs (enoblituzumab 15 mg/kg and either retifanlimab 375 mg or tebotelimab 600 mg) on a every 3 weeks (Q3W) basis, in cycles of 3 weeks duration (see **Figure 2**). The initial tumor assessment will occur at the end of Cycle 2 (i.e., after approximately 6 weeks), and at the end of every 3 cycles thereafter (i.e., approximately every 9 weeks). After receipt of the last dose of study treatment, patients will enter an Efficacy Follow-up Period and will be followed for survival.

Figure 2

An independent Data Safety Monitor (DSM), the Sponsor, and Investigators will maintain regular oversight of patient safety throughout the trial. In the Tebotelimab Cohort, toxicity will be evaluated by monitoring the occurrence and severity of DLTs in the first 12 patients (2 mini-cohorts of 6 patients each) through Cycle 2 Day 7.

The data for each of the Retifanlimab and Tebotelimab Cohorts will be analyzed upon completion of enrollment of each cohort, and after all patients in the applicable cohort have at least one tumor assessment, to inform whether to proceed with the study and to determine any modifications to the trial design.

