6.9 Pharmacokinetic, Pharmacodynamic, and Immunogenicity Parameter Endpoints Analyses

PK Analysis

Single and multiple dose PK parameters, including but not limited to C_{\max} and C_{trough} , will be derived from serum concentration versus time data. PPK analyses will be conducted using data from this study alone or combined with data from other studies. PPK and exposure-response modeling will be performed. Analysis will be conducted separately for enoblituzumab, retifanlimab, and tebotelimab.

Pharmacodynamic/Biomarker Analysis

Summary statistics for pharmacodynamic parameters will be provided and/or may be presented graphically. Possible associations between changes in pharmacodynamic measures of interest and enoblituzumab, retifanlimab, and tebotelimab dose and exposure may be explored. The distributions of PD-L1, LAG-3, and B7-H3 expression will be examined. The potential associations between the biomarkers and clinical response will be explored.

ADA Analysis

The proportion of patients who are negative for study-drug specific ADA at baseline and become positive in this assay, the proportion of patients who are negative at baseline and remain negative, and those who have positive ADA at baseline that increases or decreases in titer over the course of treatment will be summarized. Analysis will be conducted separately for enoblituzumab, retifanlimab, and tebotelimab.

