6.10 Subgroup Analyses

The primary efficacy endpoint ORR will be analyzed by the following subgroups (not limited to those listed below). A particular subgroup analysis will be performed only if there are enough patients in that subgroup to render the analysis meaningful. Further, depending on the outcomes of the trial, these listed subgroup analyses may not be performed, or additional subgroups may be added, for the purpose of CSR. The SAP will not be revised for these changes.

The subgroups are defined as:

- PD-L1 expression in Retifanlimab Cohort: $CPS \geq 20$, $CPS < 20$
- HPV p16 status: Positive, Negative
- ECOG performance status: 0, 1
- Smoking status: Current/Former, Never
- Disease status: Metastatic, Recurrent only

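### The plan lets reporting of the exploratory biomarker-response analyses depend on their results

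*SAP*

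**What the plan says.** The reporting rule is the same in Protocol 3.3 and SAP 2.3: the results of the exploratory objectives "may not be included in the Clinical Study Report or database lock unless they represent meaningful findings".

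The objectives listed directly above it include "To explore the relationships between PD-1, PD-L1, B7-H3, and LAG-3 expression on tumor cells and response". Two further objectives, also under the rule, relate peripheral biomarkers, and gene expression profiles with Fc receptor polymorphism, to clinical response.

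SAP 6.9 plans to examine the distributions of PD-L1, LAG-3 and B7-H3 expression and adds: "The potential associations between the biomarkers and clinical response will be explored". It gives no method, cut-point or reporting commitment for these associations. On timing, SAP 3.1 says that "B7-H3 and LAG-3 expression will be prospectively collected and retrospectively analyzed".

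SAP 7 says that a separate programming plan will list the tables, listings and figures intended for the study report on the basis of the analyses that the SAP describes. Protocol 10.1 provides one other outlet: "The PPK and exposure-response analyses will be the subject of separate reports".

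**The concern.** A rule that admits results to a report according to what they show is a selective-reporting rule, even when the analyses are exploratory. It matters here for two reasons.

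First, a null result would be informative. B7-H3 is the target of enoblituzumab, which both cohorts receive, and LAG-3 is one of the two targets of tebotelimab in the Tebotelimab Cohort. B7-H3 expression is not an entry requirement, yet it is to be stained in all patients (Protocol 10.2.2, SAP 5.3). Protocol 2.2 cites an inverse relation between B7-H3 expression and response to PD-1 inhibitors in lung cancer as part of the rationale, and Protocol 10.2.3 acknowledges that the link between LAG-3 and response is not well understood. Finding no association would bear on both.

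Second, a reported association can be judged only against the number of associations examined. If null results may be left out, that number may not be visible.

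**Working it through.** No sample size, power or error rate is at issue, so there is no plan figure to reproduce. The check sets the passages side by side.

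1. **What is the condition?** Protocol 3.3 and SAP 2.3 name one condition for inclusion: that the findings be meaningful. Assay timing, sample availability and data quality are not mentioned. The term is not defined, and no decision-maker or time point is given. The condition therefore depends on the result.

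2. **Does it reach the biomarker-response analyses?** Yes. Expression of PD-1, PD-L1, B7-H3 and LAG-3 against response is in the same list of exploratory objectives, in both documents.

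3. **Does another passage override it?**
   - SAP 6.9 commits to exploring the associations, not to reporting them. Protocol 14.5.3 commits to summary statistics for pharmacodynamic parameters and does not mention association with response.
   - SAP 7 points the other way, because it plans study-report tables for the analyses that the SAP describes, and 6.9 is among them. It does not say that it takes precedence over the specific exception in 2.3. The two are in tension and need reconciling.
   - Protocol 10.1 sends population PK and exposure-response to separate reports. It does not cover biomarker against response.
   - SAP 6.10 lists a PD-L1 subgroup for ORR in the Retifanlimab Cohort (CPS of at least 20 against below 20), but says that "depending on the outcomes of the trial, these listed subgroup analyses may not be performed, or additional subgroups may be added". That is outcome-dependent too.
   - Protocol 10.3 adds a further dependence, since gene expression profiling and mutational burden "may be determined retrospectively based on response, and prioritized according to the availability of archival and fresh tumor biopsy specimens".

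   No passage removes the condition.

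4. **What of the database lock?** Protocol 15.2 has the database locked and the analysis datasets generated as part of that step. If entry into the lock depends on whether the findings are meaningful, someone must look at the findings before the lock. The study is open-label (Protocol 6.2), so blinding would not prevent this. Taken literally, the lock clause reverses the order in Protocol 15.2 for these data.

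**The case against.** The strongest reply is that the sentence only permits omission. The sponsor remains free to report null results, the wording is limited to the study report and the lock, and it says nothing about publications. SAP 7 may already put the SAP 6.9 analyses on a fixed list of tables in the programming plan, which is not among the documents. Exploratory assays also often finish late, which is an ordinary reason to leave them out of the main report.

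Much of this stands. A reader might infer that null results will be suppressed, that only positive associations will appear, or that the trial cannot answer its biomarker question. The documents do not support that: they allow the outcome without requiring it, and SAP 7 leans against it. Lateness is a sound reason for omission, but it is not the reason that the sentence gives.

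PD-L1 is also a weaker example than B7-H3 or LAG-3. It is tested before enrolment and defines the cohorts, and ORR is reported by cohort. The CPS subgroup in SAP 6.10 covers it further, although that subgroup may be dropped.

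A reader might also want to attach a false-positive rate, for instance 1 − 0.95^4 = 18.5% for four independent tests at 5%. That figure should not be used:

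- It is ordinary multiplicity, the same whether null results are shown or hidden, so the fix would not change it.
- It assumes a 5% test that the documents do not specify for biomarkers, and it reads *meaningful* as p < 0.05.
- Independence is doubtful, because PD-1 and LAG-3 come from one dual stain (Protocol 10.2.3).
- In a small cohort the 5% level may be unreachable. With 3 responders in 30 (a row of Protocol Table 6) and an assumed 15/15 marker split, the smallest two-sided Fisher p-value is 2 × C(15,3) / C(30,3) = 2 × 455 / 4060 = 0.22.

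**Conclusion.** The point holds in a limited form. Both documents state a result-dependent condition for including exploratory results in the study report or database lock, and nothing else in them removes it for the biomarker-response analyses. Null associations could go unreported, and the number of analyses behind a reported association could be unknown to the reader.

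The scope is narrow. ORR, the secondary endpoints, and the safety, PK and immunogenicity summaries are untouched, and no trial decision described in the documents rests on these exploratory results. The size cannot be expressed as a percentage. How much the rule matters in practice depends on how the sponsor uses the discretion and on what the programming plan lists, neither of which can be seen here. It is a low-priority correction, worth making because it is cheap.

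**What to change.** In Protocol 3.3 and SAP 2.3, delete the clause that makes inclusion depend on meaningful findings. The shortened sentence should not stand alone, because it would then allow omission without giving any reason. Follow it with text to this effect:

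> The biomarker-response analyses named in SAP 6.9 (PD-L1, LAG-3 and B7-H3 against response), if performed, will be reported whatever the result, in the study report, a dated addendum or a named separate report. Any that are not performed will be listed with the reason. Inclusion of exploratory data in the database lock depends on assay or sample availability, not on the result. Population PK and exposure-response analyses are reported separately, as in Protocol 10.1.

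This also settles the tension with SAP 7. It does not extend a reporting duty to every exploratory assay, such as the flow cytometry or ELISpot work in Protocol 10.4, and it leaves the separate reports in Protocol 10.1 as they are.

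The cost is a short wording change in each document and one summary table. The downside is that the table will carry some null exploratory results. No patient procedure, sample size or primary analysis changes.

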3 STUDY DESIGN AND PLAN

[figure not shown]
3.1 Overall Study Design and Plan

This is a Phase 2, open label, non-randomized study in the first-line treatment of patients with recurrent or metastatic SCCHN not curable by local therapy, with no prior systemic therapy for SCCHN in the recurrent or metastatic setting (with the exception of systemic therapy completed > 6 months prior if given as part of multimodal treatment for locally advanced disease).

Approximately 80 patients will be enrolled in 2 cohorts, as shown in **Figure 1**, to receive enoblituzumab in combination with either retifanlimab (Retifanlimab Cohort, PD-L1 positive [CPS \geq 1] patients, N=50) or tebotelimab (Tebotelimab Cohort, PD-L1 negative [CPS < 1] patients, N=30). Enrollment into each cohort will occur in a non-randomized fashion. Patients may not crossover between cohorts. PD-L1 expression will be prospectively collected and prospectively analyzed. B7-H3 and LAG-3 expression will be prospectively collected and retrospectively analyzed.

Figure 1

Study Schema

[figure not shown]
Enrollment in the 2 study cohorts will occur independently in a non-randomized fashion

Dosing Regimens:
 Enoblituzumab: 15 mg/kg Q3W
 Retifanlimab: 375 mg Q3W
 Tebotelimab: 600 mg Q3W

Efficacy Outcomes
Primary: ORR
Secondary: PFS, DCR, DoR, OS

Patients will receive the assigned study drugs (enoblituzumab 15 mg/kg and either retifanlimab 375 mg or tebotelimab 600 mg) on a every 3 weeks (Q3W) basis, in cycles of 3 weeks duration (see **Figure 2**). The initial tumor assessment will occur at the end of Cycle 2 (i.e., after approximately 6 weeks), and at the end of every 3 cycles thereafter (i.e., approximately every 9 weeks). After receipt of the last dose of study treatment, patients will enter an Efficacy Follow-up Period and will be followed for survival.

Figure 2

An independent Data Safety Monitor (DSM), the Sponsor, and Investigators will maintain regular oversight of patient safety throughout the trial. In the Tebotelimab Cohort, toxicity will be evaluated by monitoring the occurrence and severity of DLTs in the first 12 patients (2 mini-cohorts of 6 patients each) through Cycle 2 Day 7.

The data for each of the Retifanlimab and Tebotelimab Cohorts will be analyzed upon completion of enrollment of each cohort, and after all patients in the applicable cohort have at least one tumor assessment, to inform whether to proceed with the study and to determine any modifications to the trial design.

3.2 Sample Size

The total sample size is planned to be approximately 80 patients, with approximately 50 and approximately 30 patients in the Retifanlimab and Tebotelimab Cohorts, respectively.

Enrollment into the Retifanlimab and Tebotelimab Cohorts will occur independently in a non-randomized fashion.

The sample size for each cohort is primarily based on providing preliminary estimation of ORR. **Table 1** provides 2-sided 95% confidence intervals (CI) for a number of potential responses.

Table 1 Response Rates and 95% Confidence Intervals

Sample Size	Number of Responses	Response Rate (%)	95% Confidence Interval (%)
30	2	6.7	0.8 – 22.1
30	3	10.0	2.1 – 26.5
30	4	13.3	3.8 – 30.7
50	10	20.0	10.0 – 33.7
50	14	28.0	16.2 – 42.5
50	16	32.0	19.5 – 46.7

ORRs of 19% and 5% were observed in first-line SCCHN patients with CPS ≥ 1 and CPS < 1 , respectively, in pembrolizumab monotherapy. In the Retifanlimab Cohort, based on an exact binomial test, 50 patients will distinguish a favorable true ORR of 36% from an unfavorable rate of 19% with 91% power and a 1-sided type 1 error rate of 0.079. Thus, at least 14 responses out of 50 patients are to be achieved. In the Tebotelimab Cohort, 3 responses out of 30 patients will have 80% confidence that the true ORR is $> 5\%$ (the lower limit of 1-sided 80% CI for the response rate is $> 5\%$).

4 ANALYSIS POPULATIONS

The study analyses will be performed on the following populations:

- **Safety Population:** All patients who received at least one dose of any study drug. This population will be used for analyses of safety, PK, pharmacodynamics, and immunogenicity. It will also be used for summary of baseline data and analyses of PFS and OS.
- **Response Evaluable Population:** All patients who received at least one dose of any study drug and had baseline radiographic tumor assessment. This population will be used for summary of tumor assessment data and analyses of responses.

